9.4.2 Primary Endpoint

The primary endpoint is the proportion of participants who progress to level >4 of the modified WHO ordinal scale due to COVID-19 by Day 14.

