6.3 Measures to Minimize Bias: Randomization and Blinding

This is an open-label study; however, the specific intervention to be taken by a participant will be assigned using an interactive voice response system (IVRS)/interactive web response system (IWRS). The site will contact the IVRS/IWRS prior to the start of study intervention

administration for each participant. The site will record the intervention assignment on the applicable case report form (CRF), if required.

Potential bias will be reduced using a central stratified randomization to assign participants into one of the study treatment arms, RESP301+SOC or SOC (control), with a randomization ratio of 2:1. Participants will be stratified by country and presence of risk factors for severe outcomes of COVID-19, based on comorbidities and age as follows:

1. Age >65 years
2. Ongoing or currently treated diabetes mellitus
3. Ongoing or currently treated hypertension
4. Ongoing or currently treated cardiovascular disease
5. Ongoing or currently treated chronic lung disease
6. Cancer history of less than 3 years, basal cell skin carcinoma excluded
7. Ongoing or currently treated chronic kidney disease

Participants will be stratified as no risk factor (none of the above criteria), one risk factor (one single of the above) or high-risk factor (2 or more of the above).

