7.1 Permanent Discontinuation of Study Intervention

It may be necessary for a participant to permanently discontinue (definitive discontinuation) study intervention. If study intervention is definitively discontinued, the participant will remain in the study to be evaluated for the Day 14 and Day 28 safety follow-ups. See the SoA (Table 1-1) for data to be collected at the time of discontinuation of study intervention and follow-up and for any further evaluations that need to be completed.

Study intervention will be permanently discontinued prior to 10 days if the participant:

- Improves to level 1 or 2 of the modified WHO ordinal scale;
- Progresses to a level > 4 of the modified WHO ordinal scale.

Additionally, study intervention should be permanently discontinued in the following circumstances:

1. Discontinuation of study intervention for abnormal liver tests should be considered if the Investigator believes that it is in best interest of the participant.
2. If, as part of normal clinical follow-up, a clinically significant change in ECG is identified, the Investigators should exercise their clinical judgement to decide whether continuing study intervention administration is in the best interest of safety of the participant.
3. AE/SAE if the Investigator believes that it is in best interest of the participant, including the following:
 - Development of significant bronchospasm * or worsening of cough that is not tolerated by the participant and leads to immediate discontinuation of the nebulization.
 - Progressive COVID-19 requiring initiation of non-invasive or invasive ventilation or high flow oxygen.
 - Development of mHb level above 3%.
 - Inability to safely continue receiving study intervention due to compromised respiratory status while off supplemental oxygen and receiving nebulized therapy (manifest by drop in SpO₂, increased respiratory rate or clinical other findings).

Refer to the SoA (Table 1-1) for data to be collected at the time of study intervention discontinuation and follow-up and for any further evaluations that need to be completed.

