** Inhaled citric acid and inhaled mannitol provoke bronchospasm in patients with bronchial hyperresponsiveness in a dose dependent pattern. Although the concentrations of mannitol and citric acid are below the provocative dose and concentration inducing bronchospasm, there is a theoretical risk that a participant may develop acute bronchospasm during the use of RESP301. Participants should therefore be monitored during RESP301 administration. In case of clinical intolerance or saturation decrease, nebulization should be immediately discontinued (see Section 7.2). Further clarification of the differences in signs and symptoms for acute bronchospasm and COVID-19 progression are provided in Table 7-1.*

Table 7-1 Differences in Signs and Symptoms for Acute Bronchospasm and COVID-19 Progression

	Acute bronchospasm related to inhaled bronchial irritant	Progression of COVID-19 lung disease to acute respiratory failure
Mechanism	Acute contraction of bronchial muscles resulting in bronchial obstruction resulting in increased ventilatory load	Cytokine storm resulting in alveolar damage resulting in gas transfer impairment
Onset	Within minutes (<15 minutes) following inhalation (no late phase since it is not an allergic IgE mediated reaction)	Within hours or days and not related to nebulization
Clinical auscultatory signs	Wheezing (almost all cases)	Bilateral rales (inconstant)
Patient history	Asthma or respiratory allergy	Age > 65 years, increased BMI, high blood pressure, cardiac diseases, etc.
Reversibility with inhaled beta mimetics	Within minutes	No

Abbreviations: BMI=body mass index; IgE=immunoglobulin E.

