9.1 Statistical Hypothesis

RESP301 reduces the rate of progression to level 5 and above in the modified WHO ordinal scale in COVID-19 (see Section 8.1.1).

This represents a composite endpoint of (i) death (level 7), (ii) hospitalized, on invasive mechanical ventilation or ECMO (level 6), or (iii) hospitalized, on non-invasive ventilation or high-flow oxygen devices (level 5).

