10.1.5 Committees Structure

An IDMC will be responsible for closely reviewing the safety and efficacy data from the interim analyses and for providing their recommendations on continuation of the study (see Sections 9.5 and 9.6).

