10.5 Appendix 5: Statistical Design Considerations

10.5.1 Some General Design Considerations

1. Binary primary endpoint: progression to critical stage/death up to Day 14
 - to be analyzed by a Cochran-Mantel-Haenszel (CMH) stratified for the factors used in the stratified randomization
 - subjects who withdraw from study treatment will be followed up until their primary endpoint outcome is known (i.e., up to Day 14 or progression to critical stage/death, whatever is first)
 - it is, therefore, not clear what current protocol synopsis text could mean: *If subjects are discharged from the hospital prior to day 14 due to improvement of the clinical status and their status on day 14 cannot be obtained, their status on day 14 for the primary endpoint will be imputed with the status on the day of discharge. and what the implications on statistical study characteristics could be. Further discussion is needed.*
2. Timing of the two planned interim analyses with stopping options is stated as

There are 2 interim analyses planned, the first interim analysis after the first 60 participants have completed day 10 of the observation period ... and a second interim analysis after 150 participants have completed day 14 of the observation period.

With the current text for the timing of the first interim analysis, it is not clear how many subjects will have been randomized at least 14 days prior to the interim data cut-off date and can therefore provide data for the binary primary endpoint (“progression to critical stage/death up to Day 14”).

For such a binary endpoint, Parexel does not recommend including any participant randomized less than 14 days prior to the interim data cut-off date (note this would be different to a study with a time-to-event endpoint) as

- for such participants not yet progressed, the outcome up to Day 14 is unknown and should not be imputed as “not progressed up to Day 14”
- for such participants progressed prior to Day 14, the outcome is known but their inclusion would bias the estimation of progression probability up to Day 14 in a upwards direction.

In order to set up the adaptive group-sequential study design, the following assumptions have been used:

- first interim analysis: a total of ≈ 39 participants randomized at least 14 days prior to data cut-off date
- second interim analysis: a total of $\approx 50\%$ of the initially planned number of participants randomized at least 14 days prior to data cut-off date.

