1.1 Synopsis

Protocol Title: An open-label, adaptive randomized, controlled multicenter study to evaluate the efficacy and safety of RESP301 plus standard of care (SOC) compared to SOC alone in hospitalized participants with COVID-19 requiring supplemental oxygen (NOCoV2)

Sponsor Protocol No.: RESP301-002

Study Phase: Phase 2/Phase 3

Sponsor: Thirty Respiratory Limited

Rationale:

This is an open-label, randomized, multicenter, parallel group, concurrent, controlled study using a sequential adaptive design. Participants will be consented and randomized 2:1 to the Investigational arm or the Control arm. Participants randomized to the Investigational arm will receive inhaled RESP301 (6 mL) administered using a nebulizer 3 times a day (TID) for up to 10 days in addition to the standard of care (SOC) while participants in the Control arm will receive SOC alone.

Objectives and Endpoints:

Objectives	Endpoints
Primary	

To evaluate efficacy of RESP301 in preventing progression of hospitalized COVID-19 participants at level 4 in the modified World Health Organization (WHO) ordinal scale into levels >4	
Proportion of participants who progress to level >4 of modified WHO ordinal scale due to COVID-19 by Day 14
Key Secondary	

To assess the effect of RESP301 as measured by room air SpO2	
Change in room air SpO2 from baseline over time

To assess the effect of RESP301 as measured by the National Early Warning Score (NEWS) 2 symptom score	
Change in NEWS 2 symptom score from baseline over time

Objectives	Endpoints

• To assess the treatment response on clinical status	
• Change from baseline on the modified WHO ordinal scale at each visit up to Day 28• Time to improvement to a lower level (<4) of modified WHO ordinal scale• Time to progression to a higher level (>4) of modified WHO ordinal scale
Additional Secondary	

• To assess the treatment response on clinical status	
• Time to hospital discharge• Incidence of mortality by Day 28
Safety	

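### The primary endpoint counts only progression attributed to COVID-19, with no attribution rule in an open-label trial, and the hypothesis and design appendix word it without that restriction

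*Protocol*

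**What the plan says.** Section 9.4.2 defines the primary endpoint by "participants who progress to level >4 of the modified WHO ordinal scale due to COVID-19 by Day 14". Table 3-1 and the synopsis carry the same restriction. The synopsis of Amendment 2, the latest version, still reads "Proportion of participants who progress to level >4 of modified WHO ordinal scale due to COVID-19 by Day 14". The copy of Amendment 2 at hand breaks off in the schedule of activities, so later sections are cited from Amendment 1. Amendment 2's table of changes lists none to the endpoint definition.

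Other places word the endpoint without a cause:

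- Section 9.1 says "This represents a composite endpoint of (i) death (level 7" and goes on to list levels 6 and 5.
- Appendix 5, section 10.5.1, has "Binary primary endpoint: progression to critical stage/death up to Day 14".
- Section 10.5.3, which governs the second interim and the re-estimation, uses progression to level >4 by Day 14.

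On blinding, section 6.3 says "This is an open-label study; however, the specific intervention to be taken by a participant will be assigned using an interactive voice response system". On oversight, section 10.1.5 names only the data monitoring committee: "An IDMC will be responsible for closely reviewing the safety and efficacy data from the interim analyses".

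On causes specific to treatment, section 7.1 says "there is a theoretical risk that a participant may develop acute bronchospasm during the use of RESP301". Its discontinuation list includes "Inability to safely continue receiving study intervention due to compromised respiratory status while off supplemental oxygen and receiving nebulized therapy" and a raised methemoglobin level.

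**The concern.** A cause-restricted endpoint needs a judgement for every escalation and every death. Here that judgement is made with the allocation known and with no stated criteria. One group of alternative causes exists in one arm only: bronchospasm from the inhaled product, desaturation during nebulisation, and treatment-related methemoglobinemia. If such an event led to high-flow oxygen, ventilation or death, the wording would score the participant the same as one who never progressed. Harm from the drug would then improve its apparent efficacy.

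The two wordings also affect the adaptive design. If conditional power and the re-estimated sample size are computed on unattributed progression while the final test uses attributed progression, the interim rules are predicting a different variable from the one finally tested.

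**Working it through.** **1. The wordings side by side**

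| Place | Use | Restricted by cause? |
|---|---|---|
| Synopsis, Table 3-1, 9.4.2 | Primary endpoint definition | Yes |
| 9.1 | Hypothesis | No; death, level 6 or level 5 |
| 10.5.1 | Design basis; 30% and 15% given as progression probabilities to Day 14 | No |
| 10.5.3 | Second interim and re-estimation | No |
| 9.4.3 | Key secondary: time to level >4 | No |

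**2. The plan's own sample size**

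Inputs from section 9.2: 30% on SOC, 15% on RESP301+SOC, 2:1 allocation (r = 2), one-sided alpha 0.025, about 80% power, 100 and 200 participants. The weighted mean rate is (0.30 + 2 × 0.15)/3 = 0.20.

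Control n = [1.96 × √(1.5 × 0.20 × 0.80) + 0.8416 × √(0.30 × 0.70 + 0.15 × 0.85/2)]² / 0.15² = (0.960 + 0.440)² / 0.0225 ≈ 87.2. This rounds up to 88, so 88 + 176 = 264.

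With continuity correction it is 97 + 194 = 291, close to the stated 300. At 100 and 200 the power is about 81% with the correction and 84.9% without. The sample size is not at fault on this point.

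**3. Effect of reclassifying RESP301 events only**

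The share f of RESP301 events attributed to something other than COVID-19 is an assumption, because the document gives none. The test is the pooled z at the final nominal one-sided level of 0.0249 (section 9.5):

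Z = (x_C/100 − x_T/200) / √[p̄(1 − p̄)(1/100 + 1/200)], with p̄ = (x_C + x_T)/300, rejecting if Z > 1.9617.

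The rejection probability is summed exactly over x_C ~ Bin(100, p) and x_T ~ Bin(200, p(1 − f)), where p is the true rate in both arms. Stratification and the interim looks are left out.

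| f | Events removed of 60 (p = 30%) | Apparent RESP301 rate | False-positive rate, p = 30% | False-positive rate, p = 20% |
|---|---|---|---|---|
| 0 | 0 | 30.0% | 2.6% | 2.6% |
| 5% | 3 | 28.5% | 4.8% | 4.2% |
| 10% | 6 | 27.0% | 8.2% | 6.5% |
| 15% | 9 | 25.5% | 13.3% | 9.7% |
| 20% | 12 | 24.0% | 20.3% | 14.1% |

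**4. Tipping point**

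Start from equal observed rates, 30/100 and 60/200.

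- At 39/200: p̄ = 69/300 = 0.23, and Z = 0.105/√(0.23 × 0.77 × 0.015) = 2.04, which is significant.
- At 40/200: p̄ = 70/300 = 0.233, and Z = 0.100/√(0.233 × 0.767 × 0.015) = 1.93, which is not.

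So 60 − 39 = 21 events would have to be reclassified to turn exactly equal observed rates into a significant result.

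**5. Equal removal from both arms**

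If the same share is removed in both arms, the false-positive rate stays at 2.6%. Power at 30% versus 15% falls from 85.1% to 80.4% at f = 10%. The error inflation in step 3 therefore comes from the imbalance between arms, not from the restriction itself.

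**The case against.** Several points on the other side stand.

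- **Not one arm only.** A reader might infer that non-COVID attributions can remove events from RESP301 alone. They cannot: bacterial superinfection or cardiac injury can be invoked in either arm. Only treatment-caused events are strictly one-sided.
- **The one-sided route is narrow for bronchospasm.** Table 7-1 describes onset within 15 minutes of inhalation and reversal within minutes, which seldom explains a move to ventilation or death. Section 5.3 also excludes uncontrolled asthma, a history of severe bronchospasm and a history of methemoglobinemia. But Table 7-1 is written for stopping treatment, not for counting the endpoint, and it does not cover desaturation off oxygen or methemoglobinemia.
- **The direction of judgement is not shown.** Under section 8.3.6, a disease-type event with a reasonable possibility of relation to treatment must be reported as an SAE. An investigator who favours the drug might prefer to blame COVID-19, which counts as a failure. Nor does the protocol say who attributes cause for the endpoint; that it is the investigator is an inference.
- **The events are not hidden.** Time to level >4 and Day 28 mortality carry no causal restriction, nebulisation intolerance is a safety endpoint, and the monitoring committee reviews safety. These would expose a discrepancy but do not protect the primary test.
- **The intent-to-treat set is intact.** A reader might say the restriction breaks the ITT comparison. Section 9.3 keeps every randomised participant in the assigned arm. What changes is the quantity estimated.
- **Shorter wording is not a second definition.** Sections 9.1 and 10.5.1 may be shorthand, and neither says any cause. Still, nothing in the protocol says which wording governs the count, and the planning rates are stated without attribution.

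**Conclusion.** The point holds in a limited form. The endpoint definition depends on cause, the trial is open-label, no attribution rule or blinded adjudication is stated, and the hypothesis and design appendix omit the restriction. As written, an escalation or death caused by RESP301 would not count against it. That follows from the text without any assumption about behaviour.

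The size does not follow from the text. Under 30% true progression in both arms and reclassification on RESP301 only, the false-positive rate runs from 2.6% with none to 20.3% with one event in five. Three of 60 expected events would take it to 4.8%, nearly double. A single headline figure should not be drawn from this. An inflation to about 15%, for example, needs some 10 of the 60 expected RESP301 events to be reclassified and none in control, and nothing in the document supports that rate.

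**What to change.** Delete the words *due to COVID-19* from the synopsis, Table 3-1 and section 9.4.2. State that the primary endpoint is any progression to level >4, including death from any cause, on or before Day 14, and use that definition in 9.1, the second interim, the re-estimation and the final test. Report COVID-attributed progression as a supportive analysis only.

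The cost is a wording change. A few unrelated escalations will count and add slight noise. The total stays at 300 provided 30% and 15% are any-cause rates. Appendix 5 states them that way, but section 9.2 refers back to the endpoint definition, so one sentence should confirm it.

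The change does not remove a separate open-label influence: the decision to start high-flow oxygen or ventilation is itself made with the allocation known.

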9.4.3 Secondary Endpoint(s)

The key secondary endpoints are:

1. Change from baseline on the modified WHO ordinal scale at each visit up to Day 28
2. Change in room air SpO₂ from baseline over time
3. Change in NEWS 2 symptom score from baseline over time
4. Time to improvement to a lower level (<4) of the modified WHO ordinal scale
5. Time to progression to a higher level (>4) of the modified WHO ordinal scale

Additional secondary endpoints are:

1. Time to hospital discharge
2. Incidence of mortality by Day 28

9.4.4 Tertiary/Exploratory Endpoint(s)

CCI

- CCI

9.4.5 Other Safety Analyses

All safety analyses will be performed on the Safety Population.

1. Safety and tolerability assessed by clinical safety laboratory measurements, physical examinations, vital signs, concomitant medications; cumulative incidence of AEs, SAEs and severe AEs
2. Incidence of participants unable to tolerate nebulization due to:
 - Reduction in SpO₂ to < 90%, unless well clinically tolerated according to Investigator's opinion
 - Other clinical signs of intolerance according to Investigator's opinion
3. Incidence of clinical bronchial hyper-responsiveness related to nebulization

9.4.5.1 Adverse Events

Adverse Events will be coded using the MedDRA coding dictionary.

The number and percentage of participants with any AE, any related AE, any SAE, any related SAE, any severe AE, and related severe AE as well as the total number of events for each category will be summarized. The number of deaths due to an AE, hospitalization due to an AE, and study discontinuation due to an AE will be summarized.

The number and percentage of participants with an AE, as well as the total number of AEs, will be summarized by SOC and preferred term. This tabulation will be repeated for related AEs, SAEs, related SAEs, severe AEs, and related severe AEs.

All AEs will be provided in patient listings. Patient listings of AEs causing discontinuation of study medication, AEs leading to death, SAEs, related AEs, and severe AEs will be produced.

9.4.5.2 Clinical Laboratory Evaluation

Baseline is defined as the last non-missing value obtained at the screening visit and prior to the first exposure to study drug. Actual values and changes from Baseline clinical laboratory tests

will be summarized by study day. If more than one laboratory result is reported per study visit per parameter, the last non-missing result will be selected for change from Baseline analysis.

Laboratory test results will be classified according to the reference ranges and clinical significance as determined by the Investigator. The number of participants with a non-missing result, the number and percentage of participants with a clinically significant result less than the lower limit of normal, non-clinically significant result more than the ULN, and clinically significant result more than the ULN will be summarized by study visit. If more than one laboratory result is reported per study day per parameter, the result yielding the most severe classification will be selected for analysis.

Categorical laboratory test results (urinalysis excluding pH) will be summarized by study visit. If more than one laboratory result is reported per study day per parameters, the result yielding the most severe classification will be selected for analysis.

Participants who had urine pregnancy test at screening and the results will be listed.

Participants with clinically significant abnormal laboratory test results will be listed. This listing will include all results of the laboratory parameter that was abnormal and determined to be clinically significant by the Investigator for a participant across study visit.

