8.2.4 Clinical Safety Laboratory Assessments

Refer to Appendix 3 for the list of clinical laboratory tests to be performed and to the SoA (Table 1-1) for the timing and frequency.

The Investigator must review the laboratory report, document this review, and record any clinically relevant changes occurring during the study in the AE section of the CRF. The laboratory reports must be filed with the source documents. Clinically relevant abnormal laboratory findings are those which are not associated with the underlying disease, unless judged by the Investigator to be more severe than expected for the participant's condition.

All laboratory tests with values considered clinically abnormal during participation in the study or within 4 days after the last dose of study intervention should be repeated until the values return to normal or baseline or are no longer considered clinically significant by the Investigator or Medical Monitor.

- If such values do not return to normal/baseline within a period of time judged reasonable by the Investigator, the etiology should be identified, where possible, and the Sponsor notified.
- All protocol-required laboratory assessments, as defined in Appendix 3, must be conducted in accordance with the Laboratory Manual and the SoA (Table 1-1).
- If laboratory values from laboratory assessments not specified in the protocol and performed at the institution's local laboratory result in the need for a change in participant management or are considered clinically relevant by the Investigator (e.g., are considered to be an SAE or an AE), then the results must be recorded in the CRF.

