9.4.5.3 Vital Signs

Baseline is defined as the last non-missing value obtained in screening and prior to the first exposure to study drug. Actual values and changes from Baseline in vital signs will be summarized by study day and study time point. All vital sign data will be presented in patient listings.

Vital sign values will be classified according to the clinical significance as determined by the Investigator. The number of participants with a non-missing result, the number and percentage of participants with a non-clinically significant result, and clinically significant result will be summarized by study visit and study time point. If more than one vital sign result is reported per study day and study time point per parameter, the result yielding the most severe classification will be selected for analysis.

Participants with clinically significant vital sign values will be listed. This listing will include all results of the vital sign parameter that was determined by the Investigator to be clinically significant for a participant across study time points.

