10.4.1 Definition of AE

AE Definition

• An AE is any untoward medical occurrence in a patient or clinical study participant, temporally associated with the use of a study intervention, whether or not considered related to the study intervention.• NOTE: An AE can therefore be any unfavorable and unintended sign (including an abnormal laboratory finding), symptom, or disease (new or exacerbated) temporally associated with the use of a study intervention.

Events Meeting the AE Definition

• Any abnormal laboratory test results (hematology, clinical chemistry, or urinalysis) or other safety assessments (e.g., ECG, radiological scans, vital signs measurements), including those that worsen from baseline, considered clinically significant in the medical and scientific judgment of the Investigator (e.g., not related to progression of underlying disease).• Exacerbation of a chronic or intermittent pre-existing condition including either an increase in frequency and/or intensity of the condition.• New conditions detected or diagnosed after study intervention administration even though it may have been present before the start of the study.• Signs, symptoms, or the clinical sequelae of a suspected drug-drug interaction.• Signs, symptoms, or the clinical sequelae of a suspected overdose of either study intervention or a concomitant medication. Overdose per se will not be reported as an AE/SAE unless it is an intentional overdose taken with possible suicidal/self-harming intent. Such overdoses should be reported regardless of sequelae.• "Lack of efficacy" or "failure of expected pharmacological action" per se will not be reported as an AE or SAE. Such instances will be captured in the efficacy assessments. However, the signs, symptoms, and/or clinical sequelae resulting from lack of efficacy will be reported as AE or SAE if they fulfill the definition of an AE or SAE.

Events NOT Meeting the AE Definition

- Any clinically significant abnormal laboratory findings or other abnormal safety assessments which are associated with the underlying disease, unless judged by the Investigator to be more severe than expected for the participant's condition.
- The disease/disorder being studied or expected progression, signs, or symptoms of the disease/disorder being studied, unless more severe than expected for the participant's condition.

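### The laboratory abnormality table in 9.4.5.2 omits low results judged not clinically significant, so the count of low values is incomplete and depends on an open-label label

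*Protocol*

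**What the plan says.** Section 9.4.5.2 sets the rule for grouping laboratory results: "Laboratory test results will be classified according to the reference ranges and clinical significance as determined by the Investigator". Besides the number of participants with a result, it names the categories to be counted at each visit: "clinically significant result less than the lower limit of normal, non-clinically significant result more than the ULN, and clinically significant result more than the ULN". When there are several results on one day, the one with the worst classification is used. On listings it says: "Participants with clinically significant abnormal laboratory test results will be listed".

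The same section also summarises observed laboratory values and their changes from baseline by study day, without reference to the investigator's label.

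Section 6.3 states the setting: "This is an open-label study". Whoever assigns clinical significance therefore knows the arm.

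On versions: the text quoted is from Amendment 1 (Version 2.0). The original protocol has the same three categories. The Amendment 2 (Version 3.0) change table lists no change to this section, although Section 9 of Version 3.0 is not in the text available.

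**The concern.** Laboratory measurements are a named safety endpoint, to be compared with standard of care alone. A reader of the abnormality table will take participants who are in none of its abnormal rows to be within range. Under the stated rule that is untrue for low results: someone with a low platelet count, haemoglobin or bicarbonate whom the investigator labels not significant falls into the same remainder as participants with normal values.

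Two things follow. First, low abnormalities are under-counted in both arms, with no bias needed. Second, whether a given low value is counted at all turns on a judgment made with knowledge of treatment. Identical values can then produce different counts in the two arms, or a real difference can be diluted.

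**Working it through.** The plan states no figure on this point, so there is nothing to reproduce. The check is mainly a comparison of texts.

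**Step 1: cells implied and cells tabulated (9.4.5.2, 9.4.5.3).**

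| Result | Judged significant | Judged not significant |
|---|---|---|
| Laboratory, below LLN | tabulated | **absent** |
| Laboratory, above ULN | tabulated | tabulated |
| Vital sign | tabulated | tabulated |

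Laboratory: 3 of 4 cells. Vital signs: 2 of 2.

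**Step 2: other routes by which a non-significant low laboratory result could be seen.**
- Listing: triggered only by clinically significant abnormal results, so not by this one.
- Worst-classification rule: it cannot rank a result that has no class.
- Observed values and changes from baseline: the result is included here whatever its label. These are arm-level summaries by day and do not count participants outside the range, so they soften the gap without closing it.

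**Step 3: how the gap behaves (illustration on assumed rates, not evidence about this trial).** The documents give no rates. Consider one parameter at one visit. Take the planned arm sizes of 200 and 100 (9.2), assume everyone has a result, and set the true share below LLN to 20% in both arms: 200 × 0.20 = 40 and 100 × 0.20 = 20.

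Counted = number low × share labelled significant. Not counted = the rest.

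| Labelled significant, RESP301 / SOC | Counted | Not counted | Apparent difference |
|---|---|---|---|
| 50% / 50% | 20/200 (10%) vs 10/100 (10%) | 20 + 10 = 30 | 0 points |
| 50% / 25% | 20/200 (10%) vs 5/100 (5%) | 20 + 15 = 35 | +5 points |
| 25% / 50% | 10/200 (5%) vs 10/100 (10%) | 30 + 10 = 40 | −5 points |
| 80% / 20% | 32/200 (16%) vs 4/100 (4%) | 8 + 16 = 24 | +12 points |

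Over true shares of 10% to 30% and the same labelling patterns, the apparent difference runs from −7.5 to +18 points, and 12 to 60 participants with low results go uncounted, although the values are identical in the two arms. The first row shows that the under-count needs no difference between arms in labelling.

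**Step 4: the same illustration with the fourth cell.** Significant plus non-significant low results sum to 40/200 and 20/100, that is 20% and 20%, under every labelling pattern.

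**The case against.** The strongest reply has four parts.

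*It is a dropped phrase, and table layout belongs in the SAP.* Shift tables and layout usually do. Here, however, the protocol itself fixes the category list and fixes it incompletely, and the same list stands in two versions. Version 3.0 also records document-wide minor language changes, so a silent correction there cannot be excluded.

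*Low values are not lost from the analysis.* This stands in part: they remain in the summaries of observed values and changes, as set out above.

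*The problem does not extend to all laboratory and vital-sign abnormalities.* This stands. A reader might infer that any abnormality judged not significant disappears. A high laboratory result keeps its own row. For vital signs, 9.4.5.3 says "Vital sign values will be classified according to the clinical significance as determined by the Investigator", but it then tabulates both classes and lists all the data.

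*A systematic bias between arms is not shown.* This also stands. A reader might infer that significance simply means not attributed to COVID-19, which would favour that label on RESP301. Section 8.2.4 says "Clinically relevant abnormal laboratory findings are those which are not associated with the underlying disease", with an exception for unexpected severity, but that concerns clinically relevant findings to be recorded as AEs. Section 10.4.1 has "considered clinically significant in the medical and scientific judgment of the Investigator (e.g., not related to progression of underlying disease", only as an example, and later speaks of significant findings that are associated with the disease. The tie is inconsistent, and neither the direction nor the size of any labelling difference can be derived.

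**Conclusion.** The point holds for laboratory results below the lower limit of normal. Followed as written, 9.4.5.2 leaves out one of four abnormal cells and keeps those participants out of the listing trigger. It thus under-counts low abnormalities and makes the remaining count depend on an unblinded judgment. This needs no assumption beyond the text and the open-label design.

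How many participants are affected is unknown. The figures in the illustration rest entirely on assumed rates and should not be cited as an expected effect. That the gap favours or harms either arm is not established; only that it allows an arm difference to arise from labelling.

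A reader might also infer that numeric limits found elsewhere in the protocol could serve as ready-made analysis cut-offs. The documents do not support this for two of them. The heart-rate value of 120 is an alarm during nebulisation, in a step marked for the active arm only and open to change by the investigator (1.3, footnote 6). Liver tests and PT/INR are named in footnote 4 of the schedule at screening only, so post-baseline ALT, bilirubin or INR counts would rest on unscheduled tests.

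The conclusion carries over to Version 3.0 on the assumption that Section 9.4.5.2 is unchanged there, as its change table indicates.

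**What to change.** 1. In 9.4.5.2, add the fourth category: results below the lower limit of normal that the investigator judges not clinically significant.
2. Add a by-arm shift table, from baseline to each participant's worst post-baseline result, classified against the reference range alone and without the investigator's label. Restrict it to parameters scheduled after baseline: CBC, chem 7, and mHb under Amendment 2. Because CBC and chem 7 follow local practice during treatment, show the number of participants tested beside each count.
3. Keep the tabulation by investigator-judged significance as supportive.

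The cost is one phrase in the protocol or SAP and a few extra tables. The results are already entered in the eCRF, and no new assessment is needed.
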